14.7. Efficacy and Endpoint Analyses

14.7.1. Response Endpoints and Analyses

For RECIST v1.1, the best overall response (BOR) will be categorized as CR, PR, SD, PD, or NE. To be qualified as BOR, CR and PR require confirmation at least 28 days (4 weeks) after initial observation of such response, and SD requires to be observed at least once after 35 days (6 weeks [- 1 week]) from the first dose of study drug.

The number and percent of participants with their BOR will be summarized. Objective response rate per RECIST v1.1 is estimated as the proportion of participants in the Response Evaluable Population who achieve BOR of CR or PR. Two-sided 95% exact binomial CIs of the response rates will be calculated.

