14.1. Determination of Sample Size

The number of participants who receive study drug cannot be determined precisely in advance. The study plans to treat up to approximately 72 participants in dose escalation. The sample size is based on a 3 + 3 design with 7 planned dose cohorts of IMGC936. Additional participants may be enrolled if a dose cohort is expanded, participants are replaced, or intermediate dose levels are evaluated

Each expansion cohort may be expanded independently following an optimal Simon's 2-stage design. The null hypothesis is that an uninteresting response rate is 9% less. The design has 80% power to detect a target response rate of 25% at the significance level of 1-sided 0.05. Following this design per cohort, the first stage of the futility assessment will be conducted in the first 13 response-evaluable participants in each expansion cohort. If no more than 1 responder is observed in an expansion cohort, no further participants will be recruited to that cohort and the null hypothesis will not be rejected. If there are at least 2 responders out of the 13 response-evaluable participants at the first stage, each may enroll an additional 26 participants to that cohort. If there are at least 7 responders out of a total of 39 response-evaluable participants, the null hypothesis will be rejected for that cohort.

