## **6.2.** Efficacy Outcome Analysis

The protocol specifies the following as exploratory analyses:

- To describe antitumor activity of IMGC936 using Response Evaluation Criteria in Solid Tumors version 1.1 (RECIST v1.1)
- To explore progression-free survival (PFS)

The number and percent of participants with their BOR will be presented. The objective response rate (ORR) will be presented together with BOR. Two-sided 95% exact binomial confidence intervals (CIs) of the response rates will be calculated using the method of Clopper—Pearson.

Percent change of tumor size from baseline over time will be summarized and presented by spider plot. The tumor size is defined as the sum of diameters of the target lesions. The best percent change of tumor size from baseline will be presented by waterfall plot.

The Kaplan-Meier method will be applied to estimate PFS and DoR curves; their median times, and PFS rates at 3 and 6 months, respectively. The method of Brookmeyer and Crowley will be used to construct 95% CIs for median time. The 95% CIs for PFS rates at each time point of interest will be calculated by normal approximation after log(-log) transformation.

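### At 7 of 39 responders the protocol rejects the 9% null, but the only planned interval for ORR still includes 9%, and no inference matched to the two-stage rule is pre-specified

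*Protocol*

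**What the plan says.** Protocol 14.1 sets the design for each cohort: "Each expansion cohort may be expanded independently following an optimal Simon's 2-stage design". The null is worded "The null hypothesis is that an uninteresting response rate is 9% less", read here as 9% or less. It continues: "The design has 80% power to detect a target response rate of 25% at the significance level of 1-sided 0.05". The first look comes after 13 response-evaluable participants: "If no more than 1 responder is observed in an expansion cohort, no further participants will be recruited to that cohort". With 2 or more responders, "each may enroll an additional 26 participants to that cohort", and the null is rejected if there are "at least 7 responders out of a total of 39 response-evaluable participants".

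Protocol 14.7.1 estimates ORR as the simple proportion in the Response Evaluable Population and adds "Two-sided 95% exact binomial CIs of the response rates will be calculated". SAP 6.2 says the same: "Two-sided 95% exact binomial confidence intervals (CIs) of the response rates will be calculated using the method of" Clopper–Pearson. Neither document provides a two-stage p-value, a two-stage interval or a 90% interval.

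SAP 4.9 and 4.10 state that no hypothesis test will be done, and SAP 1.1 says that the SAP governs the analysis. SAP 3.3 and 3.4.1 nevertheless keep the Simon design and the 2-of-13 gate, but leave out the 9%, the 25%, the 0.05 and the 7/39 rule.

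**The concern.** ORR is the primary endpoint of the expansion phase. The protocol attaches a rejection rule to it and then reports it with an interval built for another situation: a single sample of fixed size and a one-sided 0.025 error in each tail. At the smallest result that rejects, the two statements disagree. The count says that the 9% rate is rejected, while the interval says that 9% is not excluded.

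At stake is how a borderline cohort is read. Without a pre-specified interval or p-value that follows the design, the team would have to explain the disagreement, or choose another method, after seeing the result. Up to seven cohorts may run, so a borderline result in at least one of them is plausible.

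**Working it through.** **Inputs** (Protocol 14.1): n1 = 13, stop at 1 or fewer responders; 26 more participants, N = 39; reject at 7 or more; null 9%, target 25%, one-sided 0.05, power 80%. Interval (Protocol 14.7.1, SAP 6.2): two-sided 95% Clopper–Pearson.

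**Step 1. Reproduce the design.** The probability of passing stage 1 and ending with k or more responders is

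T(k, p) = Σ over x = 2 to 13 of Bin(x; 13, p) × P(X2 ≥ k − x; 26, p).

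- T(7, 0.09) = 0.0454, within the 0.05 limit.
- T(7, 0.25) = 0.809, against the stated 80%.
- Probability of stopping early at 9%: 0.671. Expected N = 13 + 26 × (1 − 0.671) = 21.6.
- A search over designs with N up to 50 finds this one to have the smallest expected N under the null.

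The plan's figures are correct.

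**Step 2. The planned interval at the boundary.** The Clopper–Pearson limits at 7/39 solve P(X ≥ 7; 39, p) = 0.025 and P(X ≤ 7; 39, p) = 0.025. They are 7.5% and 33.5%, around an observed ORR of 7/39 = 17.9%. The value 9% lies inside. At 8/39 the limits are 9.3% and 36.5%, so 9% is excluded there and at every higher count.

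**Step 3. Separate the two causes.** A two-stage interval replaces the binomial tails by T: the lower limit solves T(7, p) = a, and the upper limit solves 1 − T(8, p) = a, where a is the error in each tail.

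| Interval at 7/39 | Lower | Upper | Includes 9%? |
|---|---|---|---|
| 95% Clopper–Pearson (planned) | 7.5% | 33.5% | Yes |
| 90% Clopper–Pearson | 8.7% | 31.1% | Yes |
| 95% two-stage | 7.9% | 37.4% | Yes |
| 90% two-stage | 9.2% | 34.0% | No |

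The tail probabilities at 9% explain the pattern. Ignoring the stage 1 stop, P(X ≥ 7; 39, 0.09) = 0.0570, above 0.05, so a single-stage interval includes 9% even at the 90% level. Allowing for the stop, the tail is 0.0454. That is below 0.05 but above 0.025, so the two-stage interval excludes 9% only at the 90% level.

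**Step 4. How often it arises.** The probability of ending at exactly 7/39 is T(7, p) − T(8, p).

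| True ORR | P(exactly 7/39) | Share of all rejections |
|---|---|---|
| 9% | 2.7% | 60% |
| 15% | 11.0% | 36% |
| 20% | 11.9% | 20% |
| 25% | 7.2% | 9% |

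**Step 5. The point estimate.** Enumerating all outcomes, the bias of responders/n over all cohorts is −2.1 points at a true 9%, −2.6 at 15% and −1.6 at 25%. Among cohorts that continue to stage 2 it is +3.2 at 9% and +0.9 at 25%. The two-stage unbiased estimator (UMVUE) removes the first kind of bias but has +9.5 and +2.7 in continuing cohorts. Its root mean squared error is 7.5 against 5.8 points at 9%, 8.6 against 7.8 at 15%, and 8.8 against 9.2 at 25%.

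**The case against.** The best defence is that the interval decides nothing. Protocol 14.1 decides by counting responders, the objective is to describe ORR, and a 95% exact interval is an ordinary descriptive convention that need not agree with a one-sided 0.05 test. Under the governing SAP there is no test, so nothing is contradicted. All of this limits the impact, and the convention itself is not an error. It does not remove the point: Protocol 14.1 still states when the null is rejected, and the SAP keeps the Simon gate. If the SAP's position prevails, the single-stage 95% interval becomes the only pre-specified inference on the primary endpoint.

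A reader might also infer more than the documents support:

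- *That ignoring the stop makes a 0/13 cohort wrongly exclude 25%.* It does not. The outcome 0/13 is the lowest possible result under either method, so both solve (1 − p)^13 = 0.025 and give 24.7%. At the 90% level the limit falls to 20.6%.
- *That Clopper–Pearson loses material coverage.* For true rates from 1% to 90% in steps of 0.1 point, coverage falls below 95% at 23 of 891 values, with a minimum of 93.7% near 36.5%. At 25% it is 94.9%.
- *That the observed ORR overstates activity.* Over all cohorts it errs low. It errs high only among continuing cohorts, where the UMVUE errs about three times as far.
- *That the test is invalid.* Its exact type I error is 0.0454.

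**Conclusion.** The point holds as a reporting gap at the decision boundary. A cohort that ends at exactly 7/39 meets the protocol's rule for rejecting 9%, and the only planned interval, 7.5% to 33.5%, does not exclude 9%. That outcome has a probability of about 7% to 12% per cohort for true rates of 15% to 25%. From 8/39 upward there is no conflict. Level and stopping rule both contribute, so changing one alone would not cure it. The unresolved disagreement between Protocol 14.1 and SAP 4.9/4.10 over whether a test exists is part of the same problem.

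This rests on three assumptions: that the null means 9% or less; that exactly 13 and 39 evaluable participants are reached (neither document says how the cut-off or interval would change otherwise); and that outcomes are ordered with cohorts stopped at stage 1 ranked lowest. The decision rule, sample size and observed ORR can stand.

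**What to change.** In Protocol 14.7.1 and SAP 6.2, for each expansion cohort:

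1. Keep the observed ORR and the 95% Clopper–Pearson interval, labelled as descriptive.
2. Pre-specify alongside them the exact two-stage p-value against 9% and the 90% two-stage interval, as the inference that matches the rule in Protocol 14.1. At 7/39 these are 0.0454 and 9.2% to 34.0%.
3. Reconcile SAP 4.9 and 4.10 with Protocol 14.1. If the test is kept, carry the 9%, 25%, one-sided 0.05 and 7/39 rule into the SAP.

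The UMVUE (21.6% at 7/39, against the observed 17.9%) should not become the headline estimate. It is at most an optional supportive figure, because it trades a small downward bias overall for a larger upward bias in continuing cohorts.

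The cost is a few sentences and a few lines of code. The drawback is one more interval and a p-value in the table, with two confidence levels that need clear labels. Conduct, decision rule and sample size are unchanged.

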14.7.2. Analysis of Tumor Size Change Over Time

The tumor size is defined as the sum of diameters of the target lesions. The tumor size percent change from baseline over time will be summarized and will be presented by spider plot. The best tumor size percent change from baseline will be presented by waterfall plot.

14.7.3. Time-to-Event Endpoints and Analyses

Progression-free survival will be defined as the time from the first dose date of study drug to the date of first documented progression or death from any cause, whichever occurs first. The documented progression is determined by objective assessment of disease per RECIST v1.1. For participants who are not known to be dead or progressed at the time of data cut off for PFS analysis, the PFS will be censored at the date of the last tumor assessment. Specifically, the following censoring rules will be applied to the PFS analysis.

Table 11: Censoring Rules for Primary Analysis of PFS

Situation	Date	Outcome	
No baseline tumor assessments	First dose date	Censored	
Death prior to first scheduled tumor assessment	Date of death	Progressed	
No post-baseline tumor assessments in absence of death prior to first scheduled tumor assessment	First dose date	Censored	
Documented progression	Date of progression	Progressed	
Initiation of alternative anti-cancer treatments in absence of documented progression	Date of last tumor assessment on or prior to initiation of such treatment	Censored	
Death or documented progression immediately after missing 2 or more consecutive scheduled tumor assessments	Date of last tumor assessment prior to missed assessments	Censored	

Abbreviation: PFS: progression-free survival

DoR is defined as the time from the date of initial response (CR or PR) to the date of first documented progression or death from any cause, whichever occurs first. The DoR is calculated only for the responders. For responders who are not known to be dead or progressed at the time of data cut-off for DoR analysis, the DoR will be censored at the date of the last tumor assessment. Specifically, the last 3 situations described in Table 11 will be applied. DoR analyses will be performed only if there are enough responders to render the analyses meaningful.

The Kaplan-Meier method will be applied to estimate PFS and DoR curves; their median times, and PFS rates at 6 and 12 months, respectively. The method of Brookmeyer and Crowley (3) will be used to construct 95% CIs for median time of each time-to-event endpoint. The 95% CIs for PFS rates at each time point of interest will be calculated by normal approximation after log(-log) transformation.

15. QUALITY CONTROL AND ASSURANCE

Quality review activities will be undertaken to ensure accurate, complete, and reliable data. The sponsor and/or its representatives will do the following:

- Provide instructional material to the study sites, as appropriate.
- Sponsor a start-up training session to instruct investigators and study coordinators.
 This session will give instruction on the protocol, completion of eCRFs, and study procedures.
- Monitor protocol and GCP compliance on a regular basis (on-site visits and/or remote monitoring).
- Be available for consultation and stay in contact with the study site personnel by mail, e mail, telephone, and/or fax.
- Review and evaluate eCRF data and use standard computer checks to detect and query errors in data collection.
- Conduct a quality review of the database.

15.1. Monitoring, Auditing and Inspections

The sponsor or its designee will monitor the conduct of the trial on a regular basis throughout the duration of the study, according to the monitoring plan and in compliance with current GCP guidelines. Monitoring of the study will serve to ensure: (a) The rights and well-being of human subjects are protected; (b) The reported trial data are accurate, complete, and verifiable from source documentation; and (c) The conduct of the trial complies with the currently approved protocol/amendment(s), with GCP, and with applicable regulatory requirement(s).

The study monitor will educate site personnel on the conduct of the trial. The monitor will assess the trial site's compliance with the protocol and will periodically review and verify a sample of the participant data recorded on eCRFs against source documentation. The study monitor will also review documents that provide evidence of proper consent and eligibility of enrolled participants, compliant conduct of study procedures, administration and disposition of investigational product(s), reporting of SAEs and AEs, and continued maintenance of trial records.

The investigator will allocate adequate time to support such monitoring activities. The Investigator will also ensure that the monitor is given reasonable access to study-related documents, source documents (regardless of media) and study-related facilities (eg, investigational pharmacy, etc.). Queries may be raised if any datum is unclear or contradictory. The Investigator and site personnel must address all queries in a timely manner.

Sponsor personnel and the designee (ie, representative from the contract research organization) will review the protocol and clinical trial database with the investigator and the site staff at a site initiation visit. Monitoring procedures that comply with current GCP guidelines will be followed. On-site and/or remote monitoring will be performed by a representative of the sponsor (clinical study monitor). Review of the clinical trial database for completeness and clarity, cross-checking with source documents, and clarification of administrative matters will be performed. During

monitoring activities, the clinical study monitor will check the progress of enrollment, and ensure that study drug is being stored, dispensed, and accounted for according to specifications. Key study personnel from the site must be available to assist the clinical study monitor during these activities. The clinical study monitor will ensure that the investigation is conducted according to protocol design and regulatory requirements on a regular basis per the study monitoring plan.

The investigator must maintain source documents for each participant in the study, consisting of (but not limited to) all visit notes, laboratory data, ECGs, and the results of any other tests or assessments. The investigator must also keep the original signed informed consent form (ICF); a signed copy is given to the participant. The investigator must give the monitor access to all relevant source documents to confirm their consistency with clinical trial database entries. Full verification for the presence of informed consent, adherence to inclusion/exclusion criteria and documentation of SAEs is required. Additional checks of the consistency of source data with the clinical trial database are performed according to the study-specific monitoring plan.

Participation as an investigator in this study implies acceptance of the potential for inspection by the study sponsor/representatives, US or non-US government regulatory authorities, IRB/IEC, and applicable compliance and quality assurance offices. The investigator will permit study-related audits and inspections and will provide access to all study-related documents (eg, source documents, regulatory documents, data collection instruments, study data). The investigator will ensure the capability for inspections of applicable study related facilities (eg, pharmacy, diagnostic laboratory).

15.2. Data Collection and Management

The investigator is responsible for maintaining accurate, complete, and up-to-date records for each participant. The investigator is also responsible for maintaining any source documentation related to the study, including any films, tracings, or other media containing data pertaining to this protocol.

The anonymity of participants must be maintained. For data collection, and management purposes, participants are to be identified by participant number only. Documents that identify the participant beyond participant number (eg, participant initials) will not be submitted to the sponsor (eg, the signed informed consent document) and must be maintained in strict confidence by the investigator, except to the extent to allow auditing by the regulatory authorities, study monitor, or sponsor representatives.

Site personnel record all data for each participant through eCRFs using an EDC system provided and approved by the sponsor. Study sites must complete eCRFs for each participant in a timely manner shortly after each participant visit. As the person ultimately responsible for the accuracy of all eCRF data, the investigator must sign the Investigator's Statement in each participant's eCRF.

The EDC system automatically generates queries resulting from the computer checks embedded into the system to ensure data accuracy, quality, consistency, and completeness. Manual queries resulting from review by monitors, medical coders, and Data Management staff are also generated from within the EDC system, where they are tracked. Study sites resolve the queries

and correct the entered data accordingly. Every change to data is captured in the EDC system audit trail. Adverse events are coded using MedDRA, whereas concomitant medications are coded using the World Health Organization (WHO) Drug Dictionary. Upon completion of the study, or after reaching a pre-specified point in the study, Data Management will lock the database and generate the SAS datasets necessary for analysis and reporting. Upon completion of the study, each study site will be provided with the eCRFs for each of their participants.

16. ADMINISTRATIVE CONSIDERATIONS

16.1. Institutional Review Board or Independent Ethics Committee Approval

The investigator should provide the sponsor with a statement of compliance from the IRB/IEC indicating compliance with the applicable regulations in the region and International Council for Harmonisation of Technical Requirements for Pharmaceuticals for Human Use (ICH). Any documents that the IRB/IEC may need to fulfill its responsibilities, such as the protocol and any amendments, Investigator's Brochure, and information concerning participant recruitment, payment or compensation procedures, or information from the sponsor will be submitted to the IRB/IEC. The IRB/IEC's written approval of the study protocol and the ICFs will be in the possession of the investigator and the sponsor before the study drug is initiated at the investigator's site. The investigator will transmit the IRB/IEC's approval statement to the sponsor. This approval must include the date of review and refer to the study by protocol title and/or study number and version number and refer to the ICFs by version number or date. If the IRB/IEC or institution uses its own unique number for the protocol instead of the sponsor's number, that unique number should be noted on the approval statement. If approval of the ICFs is stamped on the forms (instead of documented in the IRB/IEC approval statement), the date of approval and/or expiration must be included.

Protocol modifications or changes may not be initiated without approval from the sponsor and prior written IRB/IEC approval (when required), except when necessary to eliminate immediate hazards to the participant. Such modifications will be submitted to the IRB/IEC; and written verification that the modification was submitted should be obtained.

The investigator must, where required by local regulations, submit the following to the IRB/IEC:

- The protocol, Investigator's Brochure, and any amendments or updates.
- The informed consent form(s) and any amendments or changes.
- Any documents given to participants or potential participants (eg, recruitment materials, diary cards) and the plan for distribution/use.
- Revisions of other documents originally submitted for review or for notification.
- Serious and/or unexpected AEs occurring during the study.
- New information that may adversely affect the safety of participants or conduct of the study.
- At minimum, an annual update and/or request for re-approval of study, unless otherwise specified by IRB/IEC.
- Protocol deviations.
- Notification when the study has been completed.
- Proof of indemnity/liability insurance.
- Other documents required by the IRB/IEC.

16.2. Ethical Conduct of the Study

The investigational study will be conducted according to the Protection of Human Patients (21 CFR [Code of Federal Regulations] 50), Institutional Review Boards (21 CFR 56), Obligations of Clinical Investigators (21 CFR 312.60–312.69), current ICH guideline for GCP (ICH E6), and all other applicable regulations.

